#### **5.5.4 Criteria for Defining the Severity of an Adverse Event**

AEs, including abnormal clinical laboratory values, will be graded using the NCI-CTCAE guidelines (version 4.03).

- CONFIDENTIAL -

The items that are not stipulated in the NCI-CTCAE (version 4.03) will be assessed according to the criteria below and entered into the eCRF:

Grade	Assessment Standard
1-Mild	Asymptomatic, or mild symptoms, clinical or diagnostic observations noted; intervention not indicated.
2-Moderate	Local or noninvasive intervention indicated.
3-Severe	Medically significant but not immediately life threatening, hospitalization or prolonged hospitalization.
4-Life Threatening	Life threatening consequences, urgent intervention indicated
5-Death	Death related to AE

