### **7.5 Analysis of Safety**

Safety analyses will be conducted using the safety population and summarized by treatment arms as treated.

Baseline laboratory results will be summarized using descriptive statistics by treatment arms. Worst toxicity grades per subject will be tabulated for selected AEs and laboratory analytes.

- CONFIDENTIAL -

Clinical safety data (including AEs, grade 3 and 4 hematologic and nonhematologic events, clinical laboratory evaluations, vital signs, ECGs and physical examinations) will be summarized by treatment groups using descriptive statistics or frequency distribution as appropriate.

Treatment-emergent period is defined as the duration of the study treatment plus 30 days. AEs occurring in this period are termed treatment-emergent AEs.

Duration of treatment and total dose administered will be summarized by treatment groups. In addition, the number and percentage of subjects with dose reduction will be tabulated.

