### **7.5.2 Laboratory Assessments**

Clinical laboratory evaluations (including hematology and serum chemistry) will be presented for each visit using descriptive statistics (n, mean, SD, median, minimum and maximum values). Change from baseline will also be presented. Shift analysis tables will present the shift from baseline for using NCI-CTCAE grade and lab reference range indicator. All clinically significant abnormal laboratory values will be recorded as AEs and graded using NCI-CTCAE guidelines. A listing of subject laboratory values will be provided.

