7.5.1 Adverse Events

The coding dictionary for this study will be MedDRA v23.0. Treatment-emergent AEs will be coded to SOC and preferred terms using MedDRA and graded using NCI-CTCAE v4.03.

Treatment-emergent AEs will be tabulated alphabetically by SOC and by preferred terms within SOC.

An overview table will include the following details per treatment group and overall:

- Number of TEAEs,
- Number and percentage of patients with TEAEs,
- Number of NCI-CTC grades 3 and 4 TEAEs,
- Number and percentage of patients with NCI-CTC grades 3 and 4 TEAEs,
- Number of drug related NCI-CTC grades 3 and 4 TEAEs,
- Number and percentage of patients with drug related NCI-CTC grades 3 and 4 TEAEs,
- Number of drug related TEAEs,
- Number and percentage of patients with causally drug related TEAEs,
- Number of serious TEAEs,
- Number and percentage of patients with serious TEAEs,
- Number of serious drug related TEAEs,
- Number and percentage of patients with serious drug related TEAEs,
- Number of TEAEs leading to death,

- Number and percentage of patients with TEAEs leading to death,
- Number of drug related TEAEs leading to death,
- Number and percentage of patients with drug related TEAEs leading to death,
- Number of TEAEs leading to withdrawal of treatment,
- Number and percentage of patients with TEAEs leading to withdrawal of treatment,
- Number of TEAEs leading to dose reduction,
- Number and percentage of patients with TEAEs leading to dose reduction,
- Number of TEAEs leading to dose interruption,
- Number and percentage of patients with TEAEs leading to dose interruption,
- Number of drug related TEAEs leading to withdrawal of treatment,
- Number and percentage of patients with drug related TEAEs leading to withdrawal of treatment.

An overview table of the TEAE of interest will describe by the number and percentage of patients with TEAEs of interest per treatment group and overall.

The number and percentage of patients with TEAEs, as classified by SOC and preferred terms will be summarized for each treatment group and overall. Summaries will be provided for:

- TEAEs
- NCI-CTC grade 3 or higher TEAEs
- drug related NCI-CTC grade 3 or higher TEAE
- drug related TEAEs,
- serious TEAEs,
- drug related serious TEAEs,
- TEAEs leading to withdrawal of treatment,
- TEAEs leading to dose reduction,
- TEAEs leading to dose interruption,
- drug related TEAEs leading to withdrawal of treatment,

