- TEAEs, excluding serious AEs, that equal to or exceed a threshold of 5.0% in any treatment group,
- TEAEs leading to death,
- drug related TEAEs leading to death,

The number and percentage of patients with TEAEs, classified by preferred terms by decreasing frequency within the overall group will also be summarized.

The number and percentage of patients with TEAEs that equal to or exceed a threshold of 5.0% in any treatment group, classified by preferred terms by decreasing frequency within the overall group, on a 6 monthly basis (0- <3 months; 3- <6 months; 6- <12 months; 12 months or more). The percentage of patients are calculated based on the number of patients still on treatment at the time point corresponding to the lower limit of the time intervals.

To adjust for the treatment duration, the number of TEAEs per 100 patients-years will be summarized, as classified by SOC and PT, per treatment group and overall. The number of TEAEs per 100 patients-years is calculated as the number of events *100 / (sum of the

treatment emergent period duration of all patients treated in the corresponding treatment group, in years).

The number and percentage of patients with TEAEs, as classified by SOC and preferred terms will also be summarized by maximum severity (reported according to NCI- CTCAE version 4.03).

In the patient count, if a patient has multiple TEAEs with the same SOC or PT, but with different severity, then the patient will be counted only once with the worst severity. However, if any of the severity values are missing then the patient will be counted only once with missing severity. In the AE count, the AEs will be presented in each category they were classified to. An AE can be reported multiple times in the AE module if its toxicity grade changes. Summaries will be provided for:

- TEAEs by NCI- CTCAE
- drug related TEAEs by NCI- CTCAE,
- serious TEAEs by NCI- CTCAE

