7.5.2 Clinical Laboratory Evaluation

Laboratory assessment will be done for the following parameters as applicable:

Hematology	Biochemistry	Other*
Red blood cell count	Albumin	Testosterone
White blood cell count	Alkaline phosphatase (ALP)	PSA**
White blood cell differential	Alanine aminotransferase (ALT)	
Hemoglobin	Aspartate aminotransferase (AST)	
Hematocrit	Blood urea nitrogen	
Platelet count	Blood urea	
	Calcium	
	Creatinine	
	Glucose	
	Phosphorus	
	Potassium	
	Sodium	
	Total bilirubin	
	Total protein	

*Testosterone and PSA will not be assessed for open-label phase.

**PSA may be taken locally for assessments affected by COVID-19.

Quantitative clinical laboratory variables (hematology, serum chemistry and testosterone), will be summarized using mean, standard deviation, minimum, maximum and median for each treatment group at each visit. Additionally, a within-patient change will be calculated as the post-baseline measurement minus the baseline measurement and summarized in the same way.

Based on the NCI-CTCAE grade of laboratory data, clinical laboratory evaluations will be summarized by grade and by visit as applicable, for their comparison to the upper limit. Shift analysis tables on the enzalutamide group will present the shift from baseline to each visit and to the highest grade among the post-baseline visits, by grade. The number and percentage of patients with an increase in grade will be summarized by visit.

Each laboratory result will also be classified as low (L), normal (N), or high (H) at each visit according to the laboratory supplied reference ranges.

Laboratory data will be displayed in listings. PSA results from local laboratory will be flagged in the listings.

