7.5.2.1 Liver Enzymes and Total Bilirubin

The following potentially clinically significant criteria for liver tests - defined as ALP, ALT, total bilirubin, AST, their combination are defined. The patient's highest value during the investigational period will be used.

Parameter	Criteria (Upper limit of normal[ULN])
ALT or AST	> 3xULN > 5xULN > 8xULN
Total Bilirubin	> 2xULN
ALT and/or AST AND Total Bilirubin ^(*)	(ALT and/or AST > 3xULN) and total bilirubin > 2xULN
ALT and/or AST AND Total Bilirubin ^(*) AND Alkaline phosphatase	(ALT and/or AST > 3xULN) and total bilirubin > 2xULN and Alk phos <2x ULN

^(*) Combination of values measured within same sample

The number and percentage of patients with potentially clinically significant values in liver enzyme and total bilirubin tests during the investigational period will be presented by treatment group and overall.

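### Two SAP safety-table rules need correcting: laboratory grade-shift tables leave out placebo, and one ungraded record removes a documented worst grade from the maximum-severity patient count

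*SAP*

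**What the plan says.** **Laboratory shifts.** Protocol 7.5.2 reads: "Shift analysis tables will present the shift from baseline for using NCI-CTCAE grade and lab reference range indicator". It names two scales and no arm. Protocol 7.5 adds that clinical safety data, laboratory evaluations included, "will be summarized by treatment groups using descriptive statistics or frequency distribution as appropriate". SAP 7.5.2 narrows this: "Shift analysis tables on the enzalutamide group will present the shift from baseline to each visit", and to the highest post-baseline grade, by grade only. For the second scale the SAP goes no further than classification: "Each laboratory result will also be classified as low (L), normal (N), or high (H) at each visit".

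**Maximum severity.** SAP 7.5.1 plans tables by maximum CTCAE severity for all, drug-related and serious treatment-emergent AEs. A patient with several events in one system organ class (SOC) or preferred term (PT) is first counted once, at the worst severity. The rule then adds: "However, if any of the severity values are missing then the patient will be counted only once with missing severity". The same section plans a separate table of "NCI-CTC grade 3 or higher TEAEs", with no statement that the missing-grade rule applies to it.

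**The concern.** The safety objective (Protocol 2.1.4, SAP 3.1.4) is a comparison with placebo plus ADT. A shift table is read by setting one arm's movement from baseline grade to worst grade beside the other's. With enzalutamide alone, the reader cannot tell a drug effect from what the disease and background ADT would produce anyway.

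The severity rule works against the table it governs. A table of maximum severity should hold each patient's highest known grade, but here one incomplete record takes precedence over a documented grade 3, 4 or 5. SAP 7.5.1 notes that one AE can be entered several times as its grade changes, so several records per patient are expected.

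**Working it through.** No figure in the plan needs reproducing here. The check sets the texts side by side, followed by simple arithmetic on the planned arm sizes.

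**Step 1: coverage of the shift tables.**

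| Item | Protocol 7.5 and 7.5.2 | SAP 7.5.2 |
|---|---|---|
| Grade shift, enzalutamide | planned | planned |
| Grade shift, placebo | planned (no arm limit) | left out |
| Reference-range shift, both arms | planned | classes derived, no shift specified |

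SAP 7.5 presents safety by treatment group as a default, but that default gives way where something else is specified, and SAP 7.5.2 does specify something else.

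**Step 2: what placebo keeps.** By-visit values and changes from baseline are given for each treatment group. By-grade summaries and counts of patients whose grade rose are not limited to one arm. Protocol 7.5 still commits to worst grades per subject for selected analytes. In SAP 7.5.2.1, "potentially clinically significant values in liver enzyme and total bilirubin tests during the investigational period will be presented by treatment group and overall". None of these cross-tabulates baseline grade against worst post-baseline grade.

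**Step 3: share of subjects without a grade-shift table.** Planned arm sizes are 120 and 60 (Protocol Synopsis, Sample Size Justification; Protocol 7.1). 60 / 180 = 33.3%. This is the size of the comparator arm, not a measure of bias. The table itself would use the safety population, which could be slightly smaller.

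**Step 4: the missing-grade rule in a hypothetical patient.** Suppose one SOC holds two records: preferred term A at grade 4 and preferred term B with no grade.

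| Display | Result |
|---|---|
| Patient count, PT A row | grade 4 |
| Patient count, PT B row | missing |
| Patient count, SOC row, SAP rule | missing |
| Patient count, SOC row, worst recorded grade | grade 4 |
| AE count in the same summary | one at grade 4, one missing |
| Separate grade 3 or higher table, SOC row | counted |

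The SOC row then disagrees with its own PT row and with the separate grade 3 or higher table. If the ungraded record were a second entry of term A, the PT row would also read missing.

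**Step 5: direction and unit size.** Compared with counting at the worst recorded grade, the SAP rule can only move patients out of graded rows, so graded patient counts can only fall. One patient is 1 / 60 = 1.67 percentage points of a placebo row, or 1 / 120 = 0.83 points of an enzalutamide row. The documents give no frequency of ungraded records, so no total can be computed.

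**The case against.** **The SAP elaborates the protocol and does not cancel it.** Protocol 7.5.2 still commits to the reference-range shift, the SAP derives the classes it needs, and table layouts sit in separate specifications (SAP 7.1) that are not available here. This stands in part. A reader might infer that neither arm will have a reference-range shift table, but the documents do not support that. They show only that the SAP does not specify one. The argument does not rescue the grade shift, where the SAP expressly names one arm.

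**Placebo laboratory data are still compared.** This is correct, as Step 2 shows. A reader might infer that laboratory safety is not compared between arms, and that would be wrong. The gap is one type of table.

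**With one grade missing, the true maximum is unknown, so calling it missing is honest.** That is the best defence of the severity rule. But the worst recorded grade is a valid lower bound, and the rule discards it in a table meant to show the maximum.

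**The effect is small and visible.** The AE count in the same summary keeps the graded event, the grade 3 or higher tables are separate, and all AEs are listed. Protocol 5.5.4 requires grading and supplies a scale for events that CTCAE does not cover. A blinded data review precedes lock (SAP 1). All of this stands. A reader might infer that severe events could vanish from the report, but they would drop only from the patient count of the maximum-severity tables.

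**Conclusion.** Both rules should be corrected. Neither affects the primary analysis or any formal test.

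- **Shift tables:** a direct mismatch between SAP and protocol. Placebo, one third of planned subjects, lacks the baseline-by-worst-grade table, and the SAP leaves the reference-range shift unspecified for both arms.
- **Missing severity:** a counting rule that contradicts the purpose of its table. It lowers graded patient counts by 1.7 points (placebo) or 0.8 points (enzalutamide) per patient affected, assuming all 60 and 120 planned subjects are dosed. The number affected is unknown and should be small.

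A reader might infer a third error from the note to SAP Table 7, which shows second primary malignancies over the whole study although routine AE collection stops earlier, and might suspect that cases arising on open-label enzalutamide would be charged to placebo. The documents do not establish this. The note can be read as displaying whatever is reported. Protocol 5.5.6 provides a late route for events judged possibly related. SAP 7.1 defaults tables to the double-blind period, and SAP Appendix 3 summarizes open-label AEs separately. It warrants a clarifying footnote at most.

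**What to change.** 1. SAP 7.5.2: produce the grade-shift tables for both arms in the safety population, and specify the reference-range shift for both arms.
2. SAP 7.5.1: count each patient at the worst non-missing grade for that SOC or PT, and use the missing category only when no grade is recorded.
3. Optional clarification, not a correction: footnote the second-malignancy table to say that routine AE collection ends 30 days after last dose (open-label included) or at new prostate cancer therapy, that later reports are limited to events judged possibly related, and that events after the first open-label dose are shown separately.

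The cost is SAP wording and programming. No protocol, CRF or data-collection change is needed, and SAP 1 allows version-controlled revision before hard lock.

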7.5.2.1 Liver Enzymes and Total Bilirubin

The following potentially clinically significant criteria for liver tests - defined as ALP, ALT, total bilirubin, AST, their combination are defined. The patient's highest value during the investigational period will be used.

Parameter	Criteria (Upper limit of normal[ULN])
ALT or AST	> 3xULN > 5xULN > 8xULN
Total Bilirubin	> 2xULN
ALT and/or AST AND Total Bilirubin ^(*)	(ALT and/or AST > 3xULN) and total bilirubin > 2xULN
ALT and/or AST AND Total Bilirubin ^(*) AND Alkaline phosphatase	(ALT and/or AST > 3xULN) and total bilirubin > 2xULN and Alk phos <2x ULN

^(*) Combination of values measured within same sample

The number and percentage of patients with potentially clinically significant values in liver enzyme and total bilirubin tests during the investigational period will be presented by treatment group and overall.

7.5.3 Vital Signs

The baseline visit is the last measurement taken prior to initial study drug administration.

Vital signs (systolic blood pressure, diastolic blood pressure, and pulse rate) including weight will be summarized using mean, standard deviation, minimum, maximum and median by treatment group at each time point. Additionally, a within-patient change will be calculated per visit as the post-baseline measurement minus the baseline measurement and summarized by treatment group at each time point. Finally based on the patient's highest value during the treatment period, a summary will present the number and percentage of patients with blood pressure elevation (systolic: ≥ 140 mmHg, ≥ 180 mmHg; diastolic: ≥ 90 mmHg, ≥ 105 mmHg), with increase from baseline (systolic: ≥ 10 mmHg, ≥ 20 mmHg; diastolic: ≥ 5 mmHg, ≥ 15 mmHg) or combination criteria (systolic: ≥ 140 mmHg & ≥ 20 mmHg increase from baseline, ≥ 180 mmHg & ≥ 20 mmHg increase from baseline; diastolic: ≥ 90 mmHg & ≥ 15 mmHg increase from baseline, ≥ 105 mmHg & ≥ 15 mmHg increase from baseline) or any of these criteria.

All vital signs results will be provided in a listing.

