## Treatment Exposure

In the double-blind portions of the combined phase 3 studies, the median duration of exposure to enzalutamide was 17.9 months and the median duration of exposure to placebo was 7.1 months. The median TEAE reporting period for the enzalutamide group was over 2-fold longer than for the placebo group, resulting in approximately 10 months of additional safety data collected for patients receiving enzalutamide compared with placebo.

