6.2 Safety Variables

Safety will be assessed by evaluation of the following variables:

- Treatment-emergent AEs (TEAEs; frequency, severity, seriousness, and relationship to study drug).
- Clinical laboratory variables (hematology, biochemistry, PSA and testosterone)
- Vital signs (systolic and diastolic blood pressure and pulse rate) and weight
- 12-lead ECG

Treatment-Emergent Adverse Event (TEAE)

A TEAE is defined as an AE that occurs or worsens at any time during the treatment emergent period. The treatment emergent period for double-blind treatment period is defined as the time interval from the first study drug intake up to 30 days after the date of the last dose of study drug, study discontinuation, the start of new antineoplastic therapy or prior to first open-label treatment, whichever occurs first. The treatment emergent period for open-label phase is defined as the time interval from the first open-label study drug intake up to 30 days after the date of the last dose of study drug, study discontinuation or the start of new antineoplastic therapy, whichever occurs first.

If AE start date is the same date as the study start, then it will be considered as a TEAE if the box '*Onset after first dose of study drug taken*' is ticked in the Electronic case report form(eCRF). If a patient experiences an event both during the pre-investigational period and during the investigational period, the event will be considered as TEAE only if it has worsened in severity (i.e. it is reported with a new start date and an increased NCI-CTCAE grade).

AE with both a missing start and stop dates, and AEs with a missing start date but has a known stop date which is on or after the first dose of study drug will be considered treatment-emergent.

AEs will be coded to SOC and preferred term using MedDRA v23.0 (or later version) and severity graded using National Cancer Institute's Common Terminology Criteria version 4.03 (NCI-CTCAE v4.03) for AEs.

Drug-Related TEAE

A drug related TEAE is defined as any TEAE with a causal relationship to study drug as assessed by the investigator in the eCRF (by answering 'YES') or with missing assessment of the causal relationship.

AEs of Special Interest

AEs of special interest are defined in Table 7

Table 7 Selection Criteria for AEs of Special Interest

Event of special interest	Selection based on MedDRA 23.0
Convulsion	Narrow SMQ of 'Convulsions'
Hypertension	Narrow SMQ 'Hypertension'

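### The table of blood-pressure elevations uses each patient's highest on-treatment value with no exposure adjustment, so unequal time on drug alone could separate the arms (minor)

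*SAP*

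**What the plan says.** SAP 7.5.3 plans three blood-pressure summaries.

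- Values at each visit: vital signs "will be summarized using mean, standard deviation, minimum, maximum and median by treatment group at each time point".
- Change from baseline, also by arm and visit.
- A threshold table: "based on the patient's highest value during the treatment period, a summary will present the number and percentage of patients with blood pressure elevation". Its rows cover absolute limits (systolic 140 and 180, diastolic 90 and 105), rises from baseline (systolic 10 and 20, diastolic 5 and 15) and combinations of the two. No person-time denominator, time-to-first-elevation analysis or common time window is given.

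Elsewhere the safety plan does deal with unequal treatment time. SAP 7.5.1 says: "To adjust for the treatment duration, the number of TEAEs per 100 patients-years will be summarized, as classified by SOC and PT". It also tabulates frequent TEAEs by interval, "on a 6 monthly basis (0- <3 months; 3- <6 months; 6- <12 months; 12 months or more", over patients still on treatment when the interval starts.

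Hypertension is an event of special interest, selected by a narrow SMQ (SAP 6.2, Table 7). The special-interest overview in SAP 7.5.1 gives "the number and percentage of patients with TEAEs of interest per treatment group and overall", with no rate.

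On exposure, Protocol 1.3 reports medians of 17.9 months on enzalutamide and 7.1 on placebo in the combined phase 3 studies, and adds: "The median TEAE reporting period for the enzalutamide group was over 2-fold longer than for the placebo group".

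**The concern.** A highest-value table compares maxima, and a maximum grows with the number of readings. Blood pressure is taken at every clinic visit on drug (Protocol 5.4.1), which Table 1 sets at days 1, 29, 57, 85 and every 28 days after that. Treatment is meant to continue to confirmed radiographic progression (Protocol 2.2.1), so its length depends on an outcome the drug is expected to delay. If the drug works, the enzalutamide arm contributes more readings per patient.

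The sponsor knows this problem. Protocol 1.3 says that adjusting for treatment duration narrowed the arm differences, with hypertension at 8.1 versus 5.4 events per 100 patient-years. The SAP carries that adjustment into the adverse-event tables but not into this one. At stake is how the measured evidence on a special-interest event is read: a raw percentage gap could be taken for a drug effect, or could enlarge a real one.

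**Working it through.** The documents give no figure for this table, so there is none to reproduce. The check asks how far the arms separate when the true blood-pressure distribution is identical in both.

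**Mechanism.** For a patient with true mean m and within-patient SD s, the chance that the highest of k readings reaches a limit c is 1 − Φ((c − m)/s)^k. With m = 130, s = 10 and c = 140, Φ(1) = 0.841. For k = 8 the chance is 1 − 0.841^8 = 75%; for k = 19 it is 1 − 0.841^19 = 96%. Averaging over patients whose means differ shrinks this gap but does not remove it.

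**Number of readings.** The pooled medians give 17.9 × 30.4375/28 = 19.5 and 7.1 × 30.4375/28 = 7.7 four-weekly visits.

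**Assumptions (none from the documents).** Mean systolic 130, between-patient SD 12, within-patient SD 8 to 12, and a baseline reading with the same noise.

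**Fixed counts, 19 versus 8 readings, no data cut.**

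| Row | Longer arm | Shorter arm |
|---|---|---|
| ≥140 | 65–81% | 54–69% |
| Rise ≥20 | 28–56% | 18–41% |
| Both | 20–48% | 12–32% |

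This is an extreme case: every patient in an arm has the same count, and the exposure is borrowed from other populations.

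**Staggered entry.** Time on drug is exponential, entry uniform over 15 months and the data cut at month 20 to 30. The Synopsis plans 15 months' recruitment plus 12 months' follow-up, which is 27. Readings are 28 days apart. The spurious excess, in percentage points, is:

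| Assumed median months on drug (enzalutamide vs placebo) | ≥140 | Rise ≥20 | Both |
|---|---|---|---|
| 18 vs 9 (design PSA-progression medians) | 4–8 | 3–8 | 2–8 |
| 33.0 vs 14.8 (radiographic PFS in the abiraterone trial, Protocol 1.1) | 4–7 | 2–7 | 2–7 |
| 39.6 vs 19.8 (ADT-alone clinical progression in the docetaxel trial, Protocol 1.1; 19.8/0.5) | 3–5 | 2–5 | 1.5–5 |
| 24 vs 16 (assumed mild gap) | 2–4 | 1–4 | 1–4 |
| Equal | 0 | 0 | 0 |

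How part-intervals and patients without a post-baseline reading are counted moves these by up to about a point. The overall span is therefore about 2 to 9 for ≥140 and 1 to 8 for the two rise rows. The ≥180 row moves by less than 1 point throughout. Diastolic rows were not simulated.

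**Crude special-interest overview.** Take the same first-event rate in both arms, 5.4 per 100 patient-years (the pooled placebo figure, treated here as a first-event rate). Over 17.9 months the crude risk is 1 − exp(−0.054 × 17.9/12) = 7.7%; over 7.1 months it is 1 − exp(−0.054 × 7.1/12) = 3.1%. That is about 2.5-fold with a true rate ratio of 1. At 12 months in both arms it is 5.3% in each.

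**The case against.** The case on the other side is substantial, and most of it stands.

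- *Hypertension is not left unadjusted.* SAP 7.5.3 compares blood pressure and its change at matched visits, which is free of the reading-count problem. SAP 7.5.1 gives TEAE rates per 100 patient-years by preferred term. A reader might infer that the plan has no exposure-adjusted or matched-time view of hypertension; the documents do not support that. What remains is narrower. By-visit means do not give the proportion over a limit, and the rates cover reported adverse events, which a raised reading becomes only under the criteria in Protocol 5.5.1. The rates are also not specified for the SMQ.
- *The excess is not inevitable.* A reader might infer that the longer arm must show more hypertension whatever happens. That requires unequal exposure, and the documents give no exposure data for this trial. Four of the five pooled studies were in castration-resistant disease. The 18 and 9 months are PSA-progression medians, and PSA progression is not among the reasons for stopping treatment in Protocol 6.1.
- *The fixed-count gaps of about 8 to 16 points overstate the likely size.* They rest on the pooled exposure and ignore the data cut.
- *Sampling noise is of similar size.* With 120 and 60 patients and a proportion near 60%, the standard error of the difference is √(0.6 × 0.4 × (1/120 + 1/60)) = 7.7 points. Noise averages to zero, however, while this bias has a known direction.
- *Liver tests.* SAP 7.5.2.1 uses the same device: "The patient's highest value during the investigational period will be used". A reader might carry the result across. No effect was computed there, and those limits (3, 5 and 8 times ULN) are remote, so the blood-pressure figures do not transfer.

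**Conclusion.** The point holds in a limited form and is minor. The threshold table in SAP 7.5.3 is unadjusted for time on drug, and so is the special-interest overview that includes the Hypertension SMQ. If enzalutamide patients are treated longer, both will lean towards an excess on enzalutamide.

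For the measured-value table the plausible size is about 2 to 9 points at systolic ≥140, about 1 to 8 for a rise ≥20 alone or with ≥140, under 1 for ≥180, and nil at equal exposure. These sizes rest on assumed blood-pressure values and assumed times on drug. The direction needs only unequal numbers of readings. No hypothesis test is attached to the table, and no efficacy conclusion depends on it.

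**What to change.** Keep the highest-value table in SAP 7.5.3, labelled supportive. For the same criteria add one of:

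- Kaplan-Meier percentages of patients with a first exceedance by arm at fixed weeks, such as 13, 25 and 49, censoring at the end of treatment; or
- first exceedances per 100 patient-years, with time counted to first exceedance or end of treatment.

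The Kaplan-Meier form is the safer of the two. Patients prone to high readings cross early, so a person-time rate falls as follow-up lengthens and can then favour the longer-treated arm.

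In SAP 7.5.1 add a rate per 100 patient-years for the Hypertension SMQ beside its crude percentage. Extending the approach to the highest-value liver criteria in SAP 7.5.2.1 is optional.

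The cost is a few extra safety tables from data already collected. Later estimates will rest on fewer patients in the shorter-treated arm, so numbers at risk should be shown.
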